7.3.3 Aim 3 Analysis

Identification of significant organization, care process, and patient factors will be embedded in analyses for Aims 1 and 2 and will be represented as covariates in final selected models for study outcomes. Whereas Aim 1 analyses seek to quantify effect estimates for $\gamma_{010}CC_{jk}$ in equation 1 above, for Aim 3 we intend to quantify γ coefficients for patient-level factors X , clinic-level factors W , and organization-level factors Z . As described above, we will iteratively optimize models using a forward stepwise selection algorithm. Summaries for unadjusted and adjusted comparisons for all variables under study will be tabulated and/or plotted accordingly. Again, Aim 3 analyses will be conducted separately for the Primary and Historical cohorts as described above.

7.3.4 Comparison between Patient Cohorts

In comparing the two cohorts with respect to Aim 1, we will test and measure whether the comparative effectiveness of the two care coordination models differs between the two cohorts (i.e., before and after COVID). For example, we might learn that the two care models were performing similarly prior to COVID, but since COVID, patients receiving attention from a social worker in the medical/social model have fared comparatively better in one or more ways. With respect to Aim 2, we will test and measure whether the core components of the comparator care models—and other factors including size of patient panels for coordination, resources available to the coordinators, duration and frequency of encounters, mode of encounter, etc.—have shifted over time or whether the individual effects of these components or factors on outcomes differ between cohorts. For example, we may learn that clinics primarily delivering care coordination in-person corresponded with better outcomes prior to COVID, but after COVID, we may learn that telemedicine is being used at greater prevalence and with similar effect as in-person care coordination services. Finally, with respect to Aim 3, we will test and measure whether organizational, community, care process, and patient factors differ between cohorts and whether any shifts in these contextual factors have had any differential effect on patient outcomes. For example, we might learn that patients are experiencing challenges with non-medical factors (i.e., “social determinants” such as housing, employment, transportation, or insurance) at greater rates now compared to before the pandemic and further that the medical/social model now has a more significant comparative effect on these patients’ outcomes, potentially as a result. Importantly, Aims 2 and 3 will help us to understand what is driving any differences in the comparative effectiveness between the two care coordination models between the two population cohorts, should they be found to exist.

To help us understand if differences we see in the Historical vs. Primary cohorts are statistically significant, we will run the same statistical model we used to calculate the association between care coordination model and a given study outcome (e.g., care quality measure) in the separate cohorts on a combined data set (including patients from both the Historical and Primary cohorts), with the addition of an interaction parameter between the patient cohort and care coordination model. A statistical (Wald) test of this interaction term in the regression will help us determine if the relationship between choice of care coordination model and a given study outcome truly differs by cohort (timing relative to COVID).

Should we find no meaningful differences in the comparative effectiveness of the care coordination models between the two patient cohorts, our study analyses will still be enhanced by having the additional patient data added by the Historical cohort. Specifically, this will allow us to conduct further analyses using the combined data, which will provide additional statistical power to detect meaningful differences in subgroup analyses or in quantifying the contributions of specific core components or contextual factors related to care coordination, which could help deepen our understanding of our Aim 2 and Aim 3 findings, in particular.

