7.2 Sample Size and Power

7.2.1 Primary Cohort Sample Size and Power

As described in Section 4, we will recruit about 397 clinics—55% with a nursing/medical and 45% with medical/social care coordination model—to participate in this study. Although we recognize that we may not fully reach it, our goal is to recruit 100% of these clinics to participate in our study. All of these clinics will be eligible to contribute to our Primary Cohort analysis. Exact numbers of eligible patients from each clinic remains unknown, but we estimate that over a 12-month accrual period (01/01/2021 to 12/31/2021), each clinic will be able to contribute 57 patients on average. Among these patients, we estimate about 45%, or 26 patients per clinic, will be covered by one of our participating health insurance plans that will be contributing utilization outcomes. In addition, we have budgeted to survey 7,000 patients with an expected response rate of at least 60%, which would correspond with about 10 or 14 patients per clinic with 100% or 75% clinic recruitment, respectively.

Figure 4 illustrates the differences in outcomes we will be powered to detect under a range of clinic participation rates (i.e., 75%, 90%, and 100%) and number of eligible patients per clinic (ranging from 10-50). Power and sample size analyses were conducted using PASS (v.19) software, assuming two-sided tests ($\alpha=0.05$) with 80% power and an intra-cluster correlation of 0.01. For the composite care quality score, all scenarios indicate sufficient power to detect a difference in the percentage of quality measures at goal (range 0-100%) of at least 1%. For the primary utilization outcome, most scenarios indicate power to detect at least a 10% difference in the number of hospitalizations and inpatient visits. For the primary patient-reported outcome, all scenarios indicate the ability to detect at least a 1 point difference in the PROMIS-10 Global Health score (mean=50, standard deviation=10). Thus, we feel confident in our plan with this adaptation to achieve sufficient power to discover meaningful differences between care coordination models across all of our primary outcome measures for the Primary Cohort.

Figure 4: Power analysis for Primary Cohort

[figure not shown]

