7.2.2 Historical Cohort Sample Size and Power

Among the 397 clinics we are recruiting for this study, 329 should be eligible to contribute patients to our Historical Cohort analysis. Exact numbers of eligible patients from clinic remains unknown, but we estimate that over a 14-month accrual period (01/01/2018 to 02/28/2019), each clinic will be able to contribute 66 patients on average. Among these patients, we estimate about 45%, or 30 patients per clinic, will be covered by one of our participating health insurance plans that will be contributing utilization outcomes.

Figure 5 illustrates the differences in outcomes we will be powered to detect under various scenarios for the Historical Cohort. Power and sample size analyses were conducted using PASS (v.19) software, assuming two-sided tests ($\alpha=0.05$) with 80% power and an intra-cluster correlation of 0.01. For the composite care quality score, all scenarios indicate sufficient power to detect a difference in the percentage of quality measures at goal (range 0-100%) of at least 1%. For the primary utilization outcome, most scenarios indicate power to detect at least a 10% difference in the number of

hospitalizations and inpatient visits. Thus, we feel confident in our plan with this adaptation to achieve sufficient power to discover meaningful differences between care coordination models across all of our primary outcome measures for the Historical Cohort.

Figure 5: Power analysis for Historical Cohort

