7.3 Analysis Plan

7.3.1 Aim 1 Analysis

To evaluate the impact of coordination type (medical/social vs. nursing/medical) on study outcomes, we will specify a series of generalized linear mixed models (GLMMs). Individual patients (nested within clinic and organization) are the primary unit of analysis. To account for patient clustering, we will incorporate a random intercept for clinic into the model. Covariates will be specific to a given model (outcome) and will be selected based on a combination of substantive knowledge, empirical evidence, and model fit statistics (e.g., Bayesian Information Criterion). Investigators will first select a set of covariates that must be included in each model. From this initial set, a forward stepwise selection algorithm will select additional covariates to include until a stopping criterion is met, and the final model specification for each outcome is identified.⁵² Random effects will be evaluated and retained in a given model based on model fit statistics and Wald tests for covariance parameters. Patient care quality outcomes for Aim 1 analyses will be modeled as binary dependent variables (e.g., meeting goal vs. not meeting goal) within subgroups based on a patient's status at the time of care coordination initiation (e.g. meeting criteria at the start of care coordination vs. not), and corresponding GLMMs will have the general form:

$$(1) \eta_{ijk} = \gamma_{000} + u_{0j0} + \gamma_{100}X_{ijk} + \gamma_{010}CC_{jk} + \gamma_{020}W_{jk} + \gamma_{001}Z_k + \varepsilon_{ijk}$$

where η represents the log-odds of a care quality outcome (e.g., BP control); γ_{000} is the intercept (value for a 'typical' patient at a 'typical' clinic); u_{0j0} is the random intercept at the clinic level; X_{ijk} is a vector of covariates (age, etc.) for patient i within clinic j and organization k ; CC_{jk} represents the exposure variable of interest, care coordination type, designated at the clinic level; W_{jk} is a vector of clinic-level covariates; and Z_k is a vector of organization-level covariates. Effect estimates will be calculated via γ coefficients (specifically γ_{010} for the relative log-odds comparing the medical/social vs. nursing/medical care coordination model); ε_{ijk} is an error term. In addition to analyses of individual care quality

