outcomes, we will also evaluate a composite outcome representing the proportion of applicable care quality outcomes that are met by a given patient. We intend to primarily evaluate this proportion as a continuous variable in a linear or tobit regression model that follows the structure in equation (1) above with the inclusion of a patient's baseline composite outcome as a covariate. However, based on the empirical distribution, we may also evaluate transformations to binary or multilevel categorical versions of this outcome as warranted.

Utilization outcomes for Aim 1 analyses will be evaluated both as binomial (any occurrence vs. none) and as counts. GLMMs will follow the framework of equation (1) above, however, for the underlying distribution of count outcomes we will assume a Poisson (or negative binomial, as appropriate) distribution with a log (as opposed to logit) link function. We anticipate a similar modeling approach for quantitative analyses of the impact of care coordination type on patient-reported outcomes (again adapting assumptions of the underlying distribution and corresponding link function, specific to the nature of each outcome variable). The main exception will be that we will not have baseline values for patient-reported measures, given that they will only be collected at a single time point in follow-up. Reporting of medical costs as a secondary outcome will follow PCORI standards.⁵³

Primary results for Aim 1 analyses will be reported as odds ratios, rate ratios, or (beta) differences (comparing the medical/social care coordination model to the nursing/medical model), with 95% confidence intervals, for each study outcome.

All Aim 1 analyses as described above will be replicated for both the Primary and Historical cohorts, and reported separately. To evaluate whether cohort-specific estimates statistically differ with respect to a given outcome, we will estimate pooled (Primary + Historical) models and evaluate the significance of the Wald test for the interaction term (*Cohort*CC Type*). Additionally, for the Historical cohort, care quality and utilization outcomes may potentially be available for up to 3 years from the onset of care coordination. Where data is available, we will estimate the impact of care coordination type on 1-year, 2-year, and 3-year outcomes respectively, using the framework described above, within the Historical cohort.

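### The pooled cohort-by-model interaction test names no clinic-by-cohort variance; if clinic effects shifted between 2018-19 and 2021, its standard error for quality and utilization outcomes will be too small

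*Combined protocol and SAP*

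**What the plan says.** Section 7.3.1 sets out the Aim 1 model for a single cohort. On clustering it says "we will incorporate a random intercept for clinic into the model", and equation (1) carries that one random term. The same paragraph adds that random effects will be assessed and kept according to fit statistics and Wald tests of the covariance parameters. It names no candidate beyond the clinic intercept.

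For the comparison of cohorts, 7.3.1 plans pooled models and will "evaluate the significance of the Wald test for the interaction term" of cohort with care coordination type. Section 7.3.4 repeats this: the same model is run on the combined data, "with the addition of an interaction parameter between the patient cohort and care coordination model". Neither section mentions a clinic-by-cohort random effect, a random cohort slope by clinic, or cluster-robust standard errors.

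Section 7.3.4 also asks whether coordination components, panel sizes, resources and encounter modes changed between the cohorts. Sections 7.3.6.2 and 7.3.6.3 limit patient-reported outcomes to the Primary Cohort, so the interaction can be tested only for care quality and utilization.

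**The concern.** Of the 397 clinics, "329 should be eligible to contribute patients to our Historical Cohort analysis". For a clinic that supplies both cohorts and keeps its model, the interaction is a within-clinic change from 2018-19 to 2021, compared between the two models. A single clinic intercept shared across the cohorts drops out of that change, so the model's standard error for the interaction reflects patient-level variation only. The cohort main effect removes the average shift over time. It does not remove the departure of individual clinics from that average.

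The study's own materials anticipate such departures. Section 1.3 describes major disruption of care. The care coordinator survey (Appendix F, question 3) asks each clinic whether coordination time was cut in 2021, with answers from no reduction up to 76-100%. The organizational survey (Appendix D, part E) asks about budget cuts. Covariates can absorb only the measured part of these changes.

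At stake is the error rate of the test that the plan uses to say whether the comparative effect of the two models changed with the pandemic. The test would be applied to each quality and utilization outcome.

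**Working it through.** **The plan's own figure.** The documents state no figure for the interaction test. The nearest stated figure with all its inputs is the 1-point detectable difference in the PROMIS-10 score (SD 10) in section 7.2.1, "assuming two-sided tests ($\alpha=0.05$) with 80% power and an intra-cluster correlation of 0.01", with clinics split "55% with a nursing/medical and 45% with medical/social care coordination model".
- Formula: detectable difference = (1.960 + 0.842) × sqrt{SD² × [1 + (m − 1) × 0.01] × (1/n1 + 1/n2)}.
- 397 clinics, m = 10: n = 3,970, design effect 1.09, standard error 0.333, detectable difference 0.93.
- 75% of clinics, m = 14: design effect 1.13, standard error 0.331, detectable difference 0.93.
- 90% of clinics, m = 10: detectable difference 0.98.

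The 1-point figure therefore reproduces at the survey yields the plan expects. Only 75% participation with 10 per clinic falls short (1.08).

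**Inputs for the interaction.**
- Primary Cohort, quality: "each clinic will be able to contribute 57 patients on average". Utilization: "we estimate about 45%, or 26 patients per clinic".
- Historical Cohort (7.2.2): 66 per clinic for quality and 30 for utilization.
- ICC 0.01 (7.2.1 and 7.2.2), a single-cohort planning value.
- f, the share of clinic variance specific to a cohort. The documents give no value, so it is an assumption, taken over its full range from 0 to 1.

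**Formula.** Total variance is scaled to 1.
- Variance of a clinic's change as the shared-intercept model sees it: e = (1 − ICC) × (1/mP + 1/mH).
- True variance: e + 2 × f × ICC.
- Ratio R = 1 + 2 × f × ICC / e.
- Actual size of the nominal 5% test = 2 × [1 − Φ(1.96/√R)].

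Quality: e = 0.99 × (1/57 + 1/66) = 0.0324. Utilization: e = 0.99 × (1/26 + 1/30) = 0.0711.

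| f | Quality R | True/reported SE | Size | Utilization R | True/reported SE | Size |
|---|---|---|---|---|---|---|
| 0 | 1.00 | 1.00 | 5.0% | 1.00 | 1.00 | 5.0% |
| 0.25 | 1.15 | 1.07 | 6.8% | 1.07 | 1.03 | 5.8% |
| 0.5 | 1.31 | 1.14 | 8.7% | 1.14 | 1.07 | 6.7% |
| 1 | 1.62 | 1.27 | 12.3% | 1.28 | 1.13 | 8.3% |

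At f = 0.5 the reported standard error for quality is 1/1.144 = 0.874 of the true one, about 13% too small.

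**Sensitivity.** With fewer patients per clinic the excess shrinks. At f = 0.5, 20/23 per clinic gives 6.3% and 10/12 gives 5.6% (illustrative sizes). With a larger ICC it grows: at 0.05 and f = 0.5, 22.5% for quality and 13.7% for utilization.

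**Simulation check.** Linear mixed models were fitted by REML to 397 clinics, 329 with both cohorts, 45% medical/social, with no true interaction. Each setting had 600 to 1,100 runs, with a Monte Carlo error of about 0.7 to 1.4 points.
- Quality, clinic intercept only: 5.2% (f = 0), 8.5% (f = 0.5), 13.8% (f = 1), and 10.4% at f = 0.5 with unequal clinic sizes (coefficient of variation 1).
- Utilization, clinic intercept only: 7.6% (f = 0.5) and 6.2% (f = 1). The excess here is small relative to simulation error, and the order of these two values is noise.
- With a clinic-by-cohort term added: 4.7% to 5.5% for quality and 3.7% to 5.4% for utilization.
- Quality, f = 0.5: the empirical SD of the estimate is 0.0220. The mean standard error is 0.0193 without the term and 0.0220 with it.

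**Would the plan's retention rule keep the term?** Take the 329 paired clinics (327 degrees of freedom) and a one-sided 5% Wald test of the variance. The test is passed when the sample variance of clinic changes exceeds e / (1 − 1.645 × √(2/327)) = 1.148 × e. The chance of that is about 38% for quality at f = 0.2 (true size without the term 6.4%), 46% for utilization at f = 0.5, and 95% for quality at f = 0.5.

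**The case against.** Several points on the other side stand.

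- **The excess is conditional.** A reader might infer that the test certainly rejects too often. The documents do not support that: if clinic effects are stable (f = 0), the planned test has its nominal size.
- **The term is unspecified, not excluded.** A reader might infer that the plan fixes a one-intercept structure. Section 7.3.1 allows random effects to be assessed, and the pooled model falls under that rule. But the rule names no clinic-by-cohort candidate, and a Wald criterion will often drop a small one, as the 38% and 46% figures show.
- **The upper figures are bounds at the plan's ICC and average clinic sizes.** The 12.3% needs zero correlation between a clinic's effects in the two cohorts, which nothing in the documents suggests. The 57 and 66 per clinic are averages over all enrolled patients. Individual quality measures apply to patients with the relevant condition and are analysed within baseline-status subgroups, so their excess is smaller.
- **The consequences are limited.** It is tempting to say the test decides whether the cohorts are pooled. Section 7.3.1 reports the cohorts separately by default. Section 7.3.4 makes further combined analyses depend on finding no meaningful difference, and describes them as added power for subgroup and component questions. Over-rejection would push towards the default.
- **The arithmetic is linear.** Binary and count outcomes would change the size of the effect but not its direction. Clinics that changed model between cohorts are not pure within-clinic contrasts.

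None of this removes the gap: the pooled model as described has no place for clinic-specific change.

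**Conclusion.** The point holds in conditional form. As written, the pooled model can represent only clinic effects that are the same in both cohorts. If those effects moved, which the plan gives good reason to expect, the interaction standard error for quality and utilization outcomes is too small. At the plan's ICC and average clinic sizes, the excess over 5% runs from nothing to about 7 percentage points for quality (12.3 − 5.0) and about 3 points for utilization (8.3 − 5.0). If half of the clinic variance is cohort-specific, it is 3.7 and 1.7 points. These figures rest on an assumed f, the single-cohort ICC of 0.01, equal clinic sizes and a linear model. A higher ICC or unequal clinic sizes would raise them; fewer patients per clinic would lower them. It should be corrected because the remedy is simple and restores nominal size, but it does not call the main Aim 1 results into question.

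**What to change.** In sections 7.3.1 and 7.3.4, state that the pooled model for quality and utilization outcomes includes a clinic-by-cohort random intercept alongside the clinic intercept. Exempt that term from the fit-statistic and Wald retention rule. Alternatively, state that the interaction will be tested with clinic-clustered robust standard errors. Either choice should be made before the pooled analysis is run.

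The cost is one extra variance component, or a different variance estimator, and a slightly wider interval for the interaction. No new data are needed.

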7.3.5 Summary of outcomes by clinic or organization

In addition to the comparative effectiveness analyses described in Sections 7.3.1-7.3.4, we will aggregate outcomes at the clinic or organizational levels using predicted margins from the appropriate analytic models described above in order to provide additional information and context to clinics or organizations to support implementation of study findings and comparisons to their peers.

[figure not shown]
7.3.6 Causal Inference

7.3.6.1 Causal model underlying the research question

[figure not shown]
The primary causal research question(s) of interest in this study is, “What is the difference in risk/probability of outcome Y for care coordination patients under the medical/social model, versus the risk/probability of outcome Y for care coordination patients under the nursing/medical model,” where Y refers to each of the designated study outcomes (quality measures, utilization, patient-reported measures). Analyses will align with the following representation of the PICOTS framework: (1) the study *population* will consist of care coordination patients in participating Minnesota primary care clinics meeting criteria for the Historical or Primary Cohorts (as described in Section 4.2.2); (2) the study *intervention* is delivery of care coordination services to high-cost/high-need patients in primary care; (3) primary *comparators* will be the medical/social model versus the nursing/medical model for delivering care coordination, which have been implemented at the clinic level; (4) several care quality measures (e.g., proportion of patients with diabetes under control), healthcare utilization measures (e.g., hospitalizations), and patient-reported measures (e.g., health status) will be independently evaluated as study *outcomes*; (5) *timing* of the source data for health care quality and utilization measures will be based on the 12 months preceding and 12 (up to 36 for Historical cohort) months following each patient’s initiation of care coordination services (i.e., to account for the pre-to-post change in outcomes at the individual level upon exposure to the intervention) and patient-reported outcomes will be obtained by survey 6-18 months after initiation of care coordination services; and (6) the *setting* will be care coordination programs in Minnesota area clinics, with study data being drawn from electronic health records (as collected and combined from clinics statewide by MN Community Measurement), insurance claims, and patient surveys.

Directed acyclic graphs (DAGs) are the epidemiologist’s primary tool for specifying an underlying causal model, its key assumptions, and potential sources of bias.⁵⁴⁻⁵⁶ Briefly, DAGs are visual representations consisting of nodes (variables or vectors) and arrows (causal relationships, or more appropriately, lack of evidence that two variables are not causally related). They are ‘directed’ in that they depict unilateral

temporal sequences (typically left to right), and ‘acyclic’ in that circular pathways cannot be included (variables cannot cause themselves). We envision that our proposed quality measure and utilization outcome models could be represented by the following DAG, where \mathbf{A} is the care coordination model a patient receives (medical/social or nursing/medical), \mathbf{Y} is a specific study outcome (quality measure or utilization measure), \mathbf{Z} is the clinic-level decision to implement one care coordination model over the other, \mathbf{L}_c and \mathbf{L}_p are vectors of measured prognostic factors at the clinic and patient level, respectively, and \mathbf{U}_c and \mathbf{U}_p are vectors of unknown or unmeasured factors at the clinic patient levels, respectively.

We are interested in quantifying $\mathbf{A} \rightarrow \mathbf{Y}$. Estimates for this relationship can be biased when there are alternative ‘backdoor’ paths from \mathbf{A} to \mathbf{Y} . In this case, we can identify multiple backdoor paths via \mathbf{L}_c , \mathbf{L}_p , \mathbf{U}_c , or \mathbf{U}_p . By conditioning on measured covariates (e.g., including them in multivariable models), we can block backdoor pathways through \mathbf{L}_c and \mathbf{L}_p . Assuming the DAG is correct, we are then susceptible to bias only through unmeasured confounders \mathbf{U}_c or \mathbf{U}_p (to the extent they exist). To address this possibility, we will attempt to identify any relevant confounders that are undocumented in the data, and calculate e-values to determine if said confounder(s) could have plausibly accounted for the observed association.⁵⁷ For analyses of patient reported outcomes (via survey), we modified the previous DAG as follows:

We now have a selection step ($S=1$) between A and Y , representing completion of the survey. All of the conditions of the previous DAG described above still apply – however, we now also have collider stratification (selection) bias, if survey responders differ from non-responders with respect to measured (L_P) or unmeasured (U_P) patient factors. To address this, we will use inverse probability (of survey response) weighting, which would effectively remove the arrow from L_P into $S=1$. We would still be potentially susceptible to bias if there is strong selection by factors in U_P ; we will conduct additional sensitivity/bias analyses to place reasonable bounds on our estimates under these conditions, and acknowledge any limitations that remain.

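### The causal question is a difference in risk, but for binary and count outcomes Aim 1 plans only odds and rate ratios, with no absolute contrast between care models

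*Combined protocol and SAP*

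**What the plan says.** Section 7.3.6.1 opens the primary causal question with "What is the difference in risk/probability of outcome Y for care coordination patients under the medical/social model", sets this against the nursing/medical model, and applies it to everything: "where Y refers to each of the designated study outcomes (quality measures, utilization, patient-reported measures").

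Section 7.3.1 sets the analysis. Individual quality outcomes are binary, "where η represents the log-odds of a care quality outcome (e.g., BP control"). On clustering, "we will incorporate a random intercept for clinic into the model". "Effect estimates will be calculated via γ coefficients", here the coefficient for care coordination type. Utilization is modelled both as any versus none and as a count with a log link. On reporting: "Primary results for Aim 1 analyses will be reported as odds ratios, rate ratios, or (beta) differences", each with a 95% confidence interval. For the composite quality score: "We intend to primarily evaluate this proportion as a continuous variable in a linear or tobit regression model".

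Section 7.3.5 does plan averaged predictions, "using predicted margins from the appropriate analytic models", but aggregates them by clinic or organization as feedback. It does not set one care model against the other.

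Sections 7.3.1 and 7.3.4 compare the cohorts by a Wald test of the cohort-by-model interaction in a pooled version of the same models.

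**The concern.** The question and the planned output are on different scales for binary and count outcomes. A conditional odds ratio or rate ratio does not state how many more patients per hundred reach goal, or how many fewer visits occur per patient-year. Sections 13.6 and 15.3.4 say the results should guide the state health department and care systems in promoting or choosing a model, and that choice turns largely on absolute effects.

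The same scale carries into the cohort comparison. Section 7.3.4 treats the absence of meaningful cohort differences as grounds for further analyses on combined data. A test on the log-odds or log-rate scale asks whether the ratio changed. It does not ask whether the difference in risk changed.

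**Working it through.** **Step 1. Which outcomes are affected** (status from Table 3, scale from section 7.3.1)

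| Outcome | Status | Planned effect measure | Absolute contrast by model? |
|---|---|---|---|
| Composite quality, linear model | Primary | Beta difference | Yes |
| Continuous survey outcomes | Primary and secondary | Beta difference, if modelled linearly | Yes |
| Emergency department visits, hospitalizations | Primary | Rate ratio (count), odds ratio (any versus none) | No |
| Individual quality measures, binary | Secondary | Odds ratio | No |

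If the tobit option is used for the composite, its coefficient is a difference in a latent score. If a binary version is used, the composite joins the affected group.

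**Step 2. From odds ratio to risk difference.** The documents give no base rate, odds ratio or risk difference for any binary outcome, so there is no stated figure to reproduce. All base rates below are assumptions for the nursing/medical group. With base rate p, RD = p·OR/(1 − p + p·OR) − p. For OR = 1.2:

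- p = 0.50: 0.60/1.10 − 0.50 = 4.5 points
- p = 0.80: 0.96/1.16 − 0.80 = 2.8 points
- p = 0.90: 1.08/1.18 − 0.90 = 1.5 points

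Conversely, a 5-point gain is OR (0.55/0.45)/(0.50/0.50) = 1.22 at 50% and (0.85/0.15)/(0.80/0.20) = 1.42 at 80%. Section 7.3.1 fits the binary quality models separately by whether the patient met the goal at the start of care coordination, so the relevant base rates may differ widely between those subgroups.

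**Step 3. Counts.** With base rate λ per patient-year, the rate difference is λ(RR − 1). The 10% relative difference in section 7.2.1 is 0.1λ in absolute terms, and the planned effect measure does not supply λ.

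**Step 4. Cohort interaction.** Inputs: Historical Cohort 329 × 66 = 21,714 patients, Primary Cohort 397 × 57 = 22,629, a 55/45 split of clinics applied to patients, and ICC 0.01 (sections 7.2.1 and 7.2.2). Design effects are 1 + 65 × 0.01 = 1.65 and 1 + 56 × 0.01 = 1.56. The check is a normal-approximation Wald test, two-sided at 0.05.

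*Same 5-point risk difference in both cohorts, assumed base rates 50% (Historical) and 80% (Primary).* The difference in log odds ratios is ln 1.417 − ln 1.222 = 0.148. Its variance is the sum over cohorts of the design effect × [1/(n₀p(1−p)) + 1/(n₁q(1−q))], where p and q are the two models' risks and n₀ and n₁ the patients under each:

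- Historical: 1.65 × (1/2,986 + 1/2,418) = 0.00123
- Primary: 1.56 × (1/1,991 + 1/1,298) = 0.00198
- SE = √0.00322 = 0.0567, so z = 2.60, and the log-odds test rejects about 74% of the time.

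If only 30% of patients qualify for the measure, it rejects about 38%. With assumed base rates of 50% and 60% and all patients, it rejects about 6%, close to nominal.

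*Same OR of 1.3 in both cohorts, assumed base rates 50% and 80%.* The risk differences are 0.65/1.15 − 0.50 = 6.5 points and 1.04/1.24 − 0.80 = 3.9 points. The log-odds test rejects at its nominal 5%, while a test of the risk differences would reject about 69%.

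**Step 5. Conditional versus marginal odds ratio.** Taking the ICC of 0.01 on the latent scale, the clinic variance is (0.01/0.99)(π²/3) = 0.033. The attenuation factor is √(1 + (16√3/(15π))² × 0.033) = 1.006, or about 0.6%. Adjustment for covariates adds to this by an amount the documents do not allow one to compute.

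**The case against.** The best defence is that the sentence in section 7.3.6.1 is general framing. It covers visit counts and 0–10 ratings, for which a difference in probability has no literal meaning, and the later discussion of the causal diagram names no scale. Rewording that sentence would also remove the inconsistency. This is fair, but rewording alone would still leave users of the results without an absolute effect.

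Three stronger readings are tempting, and the documents support none of them.

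- A reader might infer that the study never estimates any difference. The primary composite is analysed mainly as a continuous proportion and section 7.2.1 powers it on a 1-point absolute difference. Continuous survey outcomes can also give mean differences.
- A reader might infer that odds ratios are defective because they move with the base rate. An odds ratio need not do so, and risk differences depend on base rates too. Step 4 shows disagreement in both directions, so interaction depends on the scale whichever one is chosen.
- A reader might infer that the reported odds ratio applies to a typical patient at a typical clinic. Section 7.3.1 attaches that description to the intercept, not to the care-model coefficient, and the clinic intercept alone shifts the log odds ratio by only about 0.6%.

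It also stands that the individual binary quality measures are secondary, and that no document shows a large shift in base rates between cohorts. Section 2.1 describes disrupted care in 2020 but gives no outcome rates.

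**Conclusion.** The mismatch is real but limited to binary and count outcomes. Among the primary outcomes it clearly reaches emergency department visits and hospitalizations. For these, no absolute contrast between care models is planned, although the planned models could supply one.

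The practical size depends on base rates that the documents do not give. Under the assumed range of 50% to 90%, one odds ratio of 1.2 spans 4.5 down to 1.5 percentage points. The cohort test could disagree with a comparison of risk differences if base rates moved as far as 50% to 80%, and hardly at all at 50% versus 60%. The rejection rates in the check also assume full clinic recruitment and a simple two-group comparison, so they are illustrations and not forecasts.

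Nothing here makes the planned ratios wrong. The gap is in what is reported beside them.

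**What to change.** In section 7.3.1, for each binary and count outcome, add beside the odds or rate ratio the standardised risk (or visits per patient-year) under each care model and their difference with a 95% CI. Obtain these by averaging the fitted model's predictions over the cohort's covariates with the care model set to each value in turn. Respect clinic clustering in both the predictions and the interval, for example by integrating over the clinic intercept and using a cluster bootstrap or the delta method. Apply the same step to the composite if a tobit or binary version is used.

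In sections 7.3.1 and 7.3.4, report the cohort-specific differences beside the interaction Wald test, and state the scale on which the cohorts are said to differ or not. Replacing the ratios as the lead result, or moving the formal test to the difference scale, is a matter of judgement and is not required.

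The cost is SAP wording, a post-estimation step on models already planned, and somewhat longer results tables. No new data are needed.
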